IRB Study Number: 20171006

Version #, Date:

Title: Prospective Comparative Study of Non-ablative Laser with and without Lytera™ 2.0 Pigment Correcting Serum on the Appearance of Skin Tone and Photoaging

NCT: NCT03661697

Last IRB Modification and Approval: 3/25/2019

1) **Protocol Title**

Effect of Combination Laser Treatment and Skin Brightening Topical on the Appearance of Skin tone and Photoaging: A Pilot Study

2) **Objectives***

Our objective is to **determine** the effects of (1) basic skin care regimen + “active” (Lytera 2.0) vs (2) basic skin care regimen only, both groups combined with laser treatment on the **appearance** of skin tone and photoaging on the face

Our hypothesis is that combination laser + brightening cream (active arm) will **improve appearance** of skin tone and photoaging of the face when compared to combination laser + non-brightening cream.

3) **Background***

Photodamaged skin can be characterized by alterations to skin tone, fine wrinkles, and tactile roughness. These changes in skin appearance are usually due to chronic exposure to ultraviolet radiation. It is a common and often distressing skin condition that can also be difficult to treat. A wide variety of treatments are available to treat these alterations in skin such as cosmetic topicals, chemical peels, dermabrasion, cosmetic lasers, neuromodulators, and dermal fillers. Topicals are often the starting point for treatment of photodamage and can be used before, during, and after office procedures to augment outcomes for patients. Laser treatment is indicated for correction of existing mild-severe photodamage/aging skin. After treatment, patients can expect to have more uniform skin tone, improved texture, more radiant skin, minimized pore size appearance, and skin that looks and feels clear and brilliant. Results can be immediate but are also progressive, improving over multiple treatments. Clinicians have now begun to investigate the usefulness of integrating skincare products and cosmetic lasers.

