The gold standard for improving the appearance of photoaging and hyperpigmentation (specifically solar lentigines) has been a hydroquinone-containing product. Makino et al compared Lytera 2.0 (a Correcting Serum) to Hydroquinone 4% in a randomized, split-face double blind study in subjects with moderate to severe skin tone. Lytera 2.0 showed statistically significant results at 2 weeks and Hydroquinone 4% showed statistically significant results at 4 weeks. Lytera 2.0 is a cosmetic product that is for brightening the appearance of skin does not contain any hydroquinone or other ingredient classified as a drug. (Please see the Lytera 2.0 patient brochure in the attached documents).The 1927 nm fractional non-ablative

laser has also been found to be effective in treating the pigment in photo-damaged skin.

In our study, only patients with Fitzpatrick skin types I through IV will be recruited as those with a higher level than skin type IV can be prone to overproduction of melanin following certain laser types. Fitzpatrick skin type I is highly sensitive, always burns, and never tans. Type II is very sun sensitive, burns easily, and hardly tans. Type III is sensitive, sometimes burns, and tans to light brown. Type IV is minimally sun sensitive, burns minimally, and tans to moderate brown. Type V is insensitive skin, rarely burns, and tans well. Type VI is insensitive, never burns, and is deeply pigmented.

Although laser treatment and lightening skin care products have been shown to improve skin tone and photo aging, currently, there is no clinical data to support the efficacy and longevity of combination laser treatment + brightening skin care products for photoaging and skin tone. Our study will attempt to observe if combination non-ablative laser (1927 nm also known as Clear and Brilliant) and Lytera 2.0 Correcting Serum will improve the appearance of skin tone and photoaging when compared to laser alone.

4) Inclusion and Exclusion Criteria*

Inclusion criteria:

- Healthy adult male and female patients 18 years and older
- Fitzpatrick skin types I-IV
- Has at least mild mottled skin tone of the face (score of 2 or more on a 5 point skin tone scale)
- Has at least 2 areas of the face with significant roughness, dyspigmentation, or fine lines or has all these characteristics in 1 or more areas

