- Willing to refrain from using any other topical products on the face, systemic retinoids, or steroids, facial peels or other facial laser procedures throughout the duration of the study
- Willing to refrain from any cosmetic procedure including but not limited to facial surgery, dermal fillers, and neuromodulators for the duration of the study
- Willing to use only the facial skin care product regimen provided for the study
- Willing to avoid extended periods of sun exposure and the use of tanning beds during the study
- Willing to have photographs taken of the face to be used de-identified in evaluations, publications, and presentations
- For females: proof that they are not pregnant (urine pregnancy test)
- English-speaker

Exclusion criteria:

- Has any uncontrolled systemic disease (such as autoimmune disorders and

connective tissue disorders such as lupus erythematosus or Sjogren's syndrome
Has any active infection in face
Has history of any skin conditions that could interfere with treatment
Has used self-tanner recently
Is currently participating in another drug research study
Is NOT willing to refrain from using any other topical products such as skin lightening, retinoids, alpha/beta-hydroxyl acids, salicylic acid, vitamins C or D, steroids, or antibiotics on the face or systemic retinoids, steroids, facial peels, neuromodulators, dermal fillers, facial surgery, or other facial laser procedures throughout the duration of the study
For females: is pregnant
Non English-speaker

Individuals will be screened for eligibility via questionnaires that address each of the inclusion and exclusion criteria. Our final study sample will include the subjects who met the inclusion/exclusion criteria and did not voluntarily drop out of the study or develop adverse effects that prohibited them from safely completing the study. We will exclude adults unable to consent, patients under the age of 18, pregnant women, and prisoners.

5) Number of Subjects*

After recruiting our subjects, 14 patients will be randomized into either arm of the study (7 in each arm).

6) Study-Wide Recruitment Methods*

This is a single center study. We will recruit subjects from a clinical database of the practice of [name]. We will use several recruitment methods including invitation via a scripted email providing information describing the study protocol and end-points, scripted invitation telephone calls, and flyers.

7) **Study Timelines***

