One month prior to laser treatments (washout period), 14 male and female subjects with moderate hyper pigmentation and photo damage of the face will be randomized to 2 skincare regimens.

The regimens are:

- "Placebo arm" – Basic skin care regimen* (Facial Cleanser, TNS ceramide Treatment Cream (standard post-procedure moisturizer), and Essential Defense Mineral Shield Broad Spectrum SPF35 (all-physical sunscreen))
- "Lytera arm" – Basic skin care regimen + **Lytera 2.0**, which will be added between the Facial Cleanser and TNS Ceramide Treatment Cream

*The basic skin care regimen is a standard regimen used in several skincare product experiments

After cleansing the face, the patients in the Lytera arm will apply one pump of the pigment-correcting serum in a circular motion to the entire face

including the forehead, cheeks, chin, nose, and neck with care to avoid the eyes. The Lytera 2.0 is applied prior to applying moisturizer and sunscreen.

On laser treatment days, patients will come into the office without having applied any topical cream that day. Lidocaine topical may or may not be applied over the face avoiding the eyes (lidocaine use will be at discretion of Principal Investigator), and patients will be given protective goggles to shield the eyes during laser treatment. Next, the laser wand is pressed to the face and passed over the skin in various horizontal and vertical directions. Treatment takes 20 to 30 minutes.

Standardized digital photographs will be taken at baseline and at each subsequent visit using the Canfield VISIA Complexion Analysis (VISIA-CA) camera system at the highest resolution in a consistent position. Pictures will be taken before laser treatments on Visit 2 and Visit 3.

The subjects will complete an exit questionnaire after completion of the study at their last study visit (Visit 4). Through the questionnaire, we will obtain information on subject satisfaction with the study as well as their opinion of how their skin has changed. We hope to use the responses to assess efficacy of our skincare regimen and to improve future related research protocols.

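### The placebo arm gets no placebo serum and the comparator is also called laser alone, yet subjects' own opinion of skin change is meant to help assess efficacy

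*Combined protocol and SAP*

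**What the plan says.** All references are to the combined protocol and SAP.

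- **Control arm (Section 9).** It is labelled a placebo arm. Its full content is "Basic skin care regimen* (Facial Cleanser, TNS ceramide Treatment Cream (standard post-procedure moisturizer), and Essential Defense Mineral Shield Broad Spectrum SPF35 (all-physical sunscreen".
- **Lytera arm (Section 9).** It uses the same regimen plus Lytera 2.0, "which will be added between the Facial Cleanser and TNS Ceramide Treatment Cream", applied as one pump over the face and neck.
- **Subject-reported outcome (Section 9).** At the exit questionnaire, Visit 4, "we will obtain information on subject satisfaction with the study as well as their opinion of how their skin has changed". The next sentence gives the purpose: "We hope to use the responses to assess efficacy of our skincare regimen and to improve future related research protocols". A self-assessment questionnaire is also given at baseline and at the end (Sections 7 and 9).
- **Recruitment (Section 6).** Methods include "invitation via a scripted email providing information describing the study protocol and end-points".
- **Comparator.** The Section 2 objective names the basic regimen only, with laser in both groups. The Section 2 hypothesis says "when compared to combination laser + non-brightening cream". Section 3 says the combination "will improve the appearance of skin tone and photoaging when compared to laser alone".
- **Primary analyses (Section 11).** These rest on MoPASI and GAIS. Section 9 has both scales graded from photographs by one independent evaluator.

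No section says that subjects in this trial are masked. The only mention of blinding is in Section 3 and concerns a cited study.

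**The concern.** A placebo arm normally means that control subjects receive something that stands in for the active product, so that they cannot tell which arm they are in. Nothing does that here. A self-rating of skin change by someone who knows whether they were given a brightening serum reflects expectation as well as any effect. The likely direction is that of the trial's hypothesis. Section 9 nevertheless gives those ratings an efficacy role.

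The label and the Section 3 phrase add to the problem. A report that took over either would describe a comparison with placebo, or with laser alone. What the design tests is the addition of one product to laser plus a basic regimen, with subjects aware of which they received.

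**Working it through.** **1. Can subjects tell their arm?** Count the products in Section 9:

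- control arm: cleanser, ceramide cream, sunscreen = 3
- Lytera arm: 3 + 1 serum = 4

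The arms differ by one visible product and one visible step, and no dummy serum fills the gap. The invitation email describes the protocol, so control subjects may also know that the other arm gets a serum. With 2 × 7 = 14 subjects, this applies to all 14. It is an inference from the regimen lists. The email script, consent form and questionnaires are not available to check what subjects are told.

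**2. Is the comparator laser alone?** Subjects start their regimens at the washout and continue until Visit 4. By nominal visit spacing that is 4 + 3 + 4 = 11 weeks of cleanser, moisturiser and sunscreen in the control arm, apart from laser days, when topicals are held (Section 34). The descriptions compare as follows:

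| Description | Where | Fits the control regimen? |
|---|---|---|
| Basic regimen only, with laser | Section 2, objective | Yes |
| Laser plus a non-brightening cream | Section 2, hypothesis | Compatible: the regimen includes a ceramide cream |
| Laser alone | Section 3 | No |
| Placebo arm | Section 9 | No: nothing replaces the serum |

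**3. Which outcomes are exposed?** The exit and self-assessment questionnaires are rated by the subjects themselves, so they are exposed. MoPASI and GAIS, as Section 9 describes them, are graded by someone else from photographs, so a subject's own expectation does not enter the score directly.

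**4. How large could it be?** The documents give no expectation effect, no standard deviation for the questionnaires and no test for them, so no size can be derived. For illustration only, assume a two-sided 5% t test between arms, normally distributed self-ratings, no true serum effect and an expectation shift of *b* SD. With 7 per arm the degrees of freedom are 12, the critical value is 2.179 and the noncentrality is *b* × √(7/2) = 1.871*b*. Then:

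- chance of a significant result favouring the serum = 1 − F(2.179), with F the noncentral t distribution function
- chance that the observed difference favours the serum = Φ(1.871*b*)

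| Assumed shift *b* (SD) | Significant, favouring serum | Difference favours serum |
|---|---|---|
| 0 | 2.5% | 50% |
| 0.3 | 7.5% | 71% |
| 0.5 | 13.6% | 82% |
| 0.8 | 28.0% | 93% |
| 1.0 | 40.6% | 97% |

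Neither the shift nor the test is in the plan. The table shows only that, in 14 subjects, a modest shift would usually make the self-ratings point towards the serum. Any effect size estimated from self-ratings for a later study, which is the purpose Section 11 gives for the analysis, would carry the shift in full.

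**The case against.** The strongest reply is that little rests on the questionnaire. The primary analyses use photo-graded scales. No test is assigned to the questionnaire responses, and they do not appear among the data items listed in Sections 9 and 10. The sentence at issue expresses a hope, speaks of a skincare regimen without naming an arm, and also aims at improving later protocols. The placebo label stands in quotation marks with its contents given at once, and nowhere does the protocol claim that subjects are masked. A pilot may be open to subjects.

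Most of this stands, and it limits the point to a supportive outcome and to wording. It does not remove the point. Section 9 expressly gives subjects' opinions an efficacy role, and the same section states the aim as observing the effect of Lytera 2.0. The label still claims a property that the design lacks.

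A reader might infer more than the documents support:

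- **That the main efficacy result is biased because subjects know their arm.** Subjects do not grade MoPASI or GAIS. Whether the photo evaluator is masked is not stated. That is a separate gap, and silence does not show that the evaluator knows the arm.
- **That a between-arm test of self-ratings is planned.** None is specified. Section 11 speaks only of comparing scores with baseline. Misattribution is a risk, not a planned analysis.
- **That all four comparator descriptions conflict.** Both Section 2 descriptions fit the design.
- **That the protocol claims an effect of particular ingredients.** Sections 2 and 9 stay at the level of the product.

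**Conclusion.** The point holds for the subject-reported outcome and for two pieces of terminology. The control arm has no placebo serum, so all 14 subjects can readily infer their arm, and their exit opinions cannot separate serum effect from expectation. Laser alone in Section 3 contradicts the control regimen in Section 9.

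The direction of bias, towards Lytera, is a judgement that subjects given a brightening serum expect to look better. Its size is unknown, and the illustrative percentages should not be cited as an estimate. The conclusion that the primary scores are not directly affected assumes that both scales are graded from photographs, as Section 9 says. The Section 7 schedule also marks these evaluations at each visit. No sample size, primary score or primary analysis changes. What changes is what may be concluded from the questionnaires and how the comparison is described.

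**What to change.** **Section 9**

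- Rename the control group *basic regimen arm*.
- State that subjects are not masked to their regimen.
- Replace the efficacy sentence with, for example: *Exit and self-assessment responses will be reported descriptively by arm as unmasked, supportive data and will not be taken as evidence of serum efficacy.* The self-assessment keeps its own name. It is also given at baseline, so calling it a satisfaction measure would be wrong.

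**Section 3**

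- Replace laser alone with *laser plus basic skin care regimen*, to match the Section 2 objective. The Section 2 wording can stay.

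The cost is protocol wording only, with no new product, visit or subject. The downside is that subject-reported results lose weight as efficacy evidence in a study of appearance. A vehicle serum would be the design alternative if that evidence is wanted, but the correction does not depend on it.

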Local tolerability including itching, redness, burning, or pain will be assessed at each visit by the investigator. Subjects will also be asked to assess discomfort during treatment and also to maintain diary at home to record any side effects after each facial laser treatment. To lessen the probability of risks of laser treatment, will use the standard pulse energy and coverage known to produce the minimal amount of side effects, increase subject comfort, and allow for rapid healing.

Once all subjects have completed the study, one independent evaluator will retrospectively analyze the VISIA high definition photography data that was taken at each visit. The independent observer will evaluate the photos of each patient for clinical efficacy and tolerability using two validated grading scales (Modified Pigmentation Area and Severity Index (MoPASI) and Global Aesthetic Improvement Scale (GAIS)) at baseline and at weeks 5, 8, and 12.

The GAIS is used to evaluate change in aesthetics after intervention. 0 = worse, 1 = no change, 2 = improved, 3 = much improved, 4 = very much improved. The MoPASI is a dermatologist-developed modified scale derived from the validated Melasma area and severity index scale. Pigmentation is assessed in 4 sections of the facial skin, and three variables are assessed within each region: percentage of area involved, darkness of pigment in the area, and pattern of involvement in the area. Subjects will complete self-

assessment questionnaires at baseline and at the end of the study.

The Clear and Brilliant 1927nm laser has been used extensively in facial cosmetic surgery for skin resurfacing to improve the skin changes associated with photoaging and skin tone. The laser is FDA approved for this use (see Device attachments for documentation). The Solta Medical Company has proven that it produces safe and effective treatment and even in combination with topicals, has a high safety profile (see supporting documents).

Lytera 2.0 Correcting Serum, a Skin Medica product, is a non-hydroquinone, non-drug advanced Correcting Serum that has been proven to minimize the appearance of skin discoloration and dark spots. Our proposed study is to observe the effect of Lytera 2.0 on skin tone, and will not evaluate any underlying changes to skin structure or function. The assessments in the proposed study are observational and do not include biopsy or other method.

Key ingredients of Lytera 2.0 Pigment Correcting Serum:

Tranexamic Acid

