Phenylethyl Resorcinol

Niacinamide and Tetrapeptide 30

Marinen Extract blend

Phytic Acid

Other ingredients: Vitis Vinifera SCE, Plankton Extracts, Hydroxyacetophenone, Artemisia Capillaris, Marine Exopolysaccharides

Data that will be collected about subjects (see attached data collection form):

Age

Gender

Race

Past medical history including current and past illnesses, current medications, allergies, past surgeries, any past adverse effects to facial cosmetics, family history, social history including alcohol, tobacco, or illicit drug use.

Past skin care history including any surgical cosmetic procedures, fillers, injectables, lasers, or topical treatments.

Fitzpatrick skin type (I-IV)

Evaluation of baseline skin tone

Adverse effects experienced throughout the study

MoPASI scores

GAIS scores

Representative photographs of subjects at baseline and at subsequent visits

10) **Data and Specimen Banking***

Data will be stored on Box, a secure file sharing, storage, and collaboration system using a password-protected, encrypted laptop. Data will be stored for 1 year after the completion of the study. Only [name], principal investigator and [name] and [name], co-investigators and study coordinator will have access to the data. Data will only be released by Drs. [name] or [name] for publication of study results.

Stored data will include:

Age

Gender

Race

Past medical history including current and past illnesses, current medications, allergies, past surgeries, any past adverse effects to facial cosmetics, family history, social history including alcohol, tobacco, or illicit drug use.

Past skin care history including any surgical cosmetic procedures, fillers, injectables, lasers, or topical treatments.

Fitzpatrick skin type (I-IV)

Evaluation of baseline skin tone

Adverse effects experienced throughout the study

MoPASI scores

GAIS scores

Representative photographs of subjects at baseline and at subsequent visits

11) **Data Management***

Statistical analysis will be conducted to determine the effect size necessary to power a study. All statistical tests will be two-sided and interpreted at a 5% significance level. The primary analyses will be based on the MoPASI and GAIS scores. Scores after each laser treatment will be compared to baseline scores using the appropriate statistical test.

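### One evaluator scores the stored photographs, and the plan specifies neither a repeat read nor an intra-rater reliability check for a subjective primary score in a 14-subject pilot

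*Combined protocol and SAP*

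**What the plan says.** Section 9 (Procedures Involved) gives the photographic scoring to a single person, after the last subject has finished: "one independent evaluator will retrospectively analyze the VISIA high definition photography data that was taken at each visit". It adds: "The independent observer will evaluate the photos of each patient for clinical efficacy and tolerability using two validated grading scales". The two scales are MoPASI and GAIS. MoPASI asks for three judgements (area, darkness, pattern) in each of four facial sections, and its origin is given as follows: "The MoPASI is a dermatologist-developed modified scale derived from the validated Melasma area and severity index scale". GAIS grades change after the intervention.

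Section 11 (Data Management) states: "The primary analyses will be based on the MoPASI and GAIS scores". It gives the purpose of the analysis as: "Statistical analysis will be conducted to determine the effect size necessary to power a study". Section 5 sets 14 subjects, 7 per arm.

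No section states how many times each photograph is read. None describes a second read, averaging, a reading order or a check of intra-rater reliability, and none gives a reliability figure or an SD for either scale. The evaluator is called independent; masking to arm or visit is not stated.

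Two other places bear on when scores are made. The schedule in section 7 lists MoPASI and GAIS evaluations at all four visits. Section 12 has efficacy data from the scale scores reviewed after each visit.

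**The concern.** A score built from twelve visual judgements (3 variables x 4 facial sections) will vary when the same person reads the same image again. If each image is read once, that variation passes in full into the MoPASI scores at baseline and follow-up, and into the SD that the pilot hands to the next study. Nothing in the plan would show how large it is.

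Two things are at stake. One is precision, which is already very limited at 7 per arm. The other is planning: without an intra-rater figure, the designers of the next study cannot separate reader noise from differences between subjects, or decide how many reads per image to use. Because the images are stored and scored at the end, a second pass by the same evaluator is possible without a new reader, visit or procedure.

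**Working it through.** The plan contains no power, SD or reliability figure, so there is nothing to reproduce. The check asks what a second averaged read would be worth.

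**Inputs from the documents.** 14 subjects, 7 per arm (section 5); four photographic visits (sections 7 and 9), so 14 x 4 = 56 photo sets if nobody drops out; one evaluator (section 9); two-sided 5% tests (section 11).

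**Assumptions.** R is the reliability of one MoPASI read, meaning agreement of the same reader with himself or herself on the same image: 0.5 to 0.9, with 0.95 as a further case. rho is the true (error-free) baseline to Visit 4 correlation: 0.6 to 0.8. c is the correlation between the errors of the two reads: 0 (independent) or 0.5 (the reader partly repeats the first score).

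**Formulas**, with the single-read variance set to 1:

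- Variance of the mean of two reads: v = R + (1 - R)(1 + c)/2.
- Unadjusted Visit 4 comparison: cut = 1 - v; equivalent N = 14/v.
- Baseline-adjusted residual variance, one read: 1 - (rho x R)^2.
- Baseline-adjusted residual variance, two reads: v - (rho x R)^2/v. The equivalent N is 14 times the ratio of the one-read to the two-read value.

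**Worked case, R = 0.7, rho = 0.8.** One read: 1 - 0.56^2 = 0.6864. Two reads, c = 0: v = 0.85, and 0.85 - 0.3136/0.85 = 0.4811. The cut is 1 - 0.4811/0.6864 = 29.9%, and 14 x 0.6864/0.4811 = 20.0 subjects. With c = 0.5: v = 0.925, and 0.925 - 0.3136/0.925 = 0.5860. The cut is 14.6%, or 16.4 subjects.

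**Variance cut (equivalent N):**

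| R | Unadjusted, c = 0 | Adjusted, rho 0.6, c = 0 | Adjusted, rho 0.8, c = 0 | Unadjusted, c = 0.5 | Adjusted, rho 0.6, c = 0.5 | Adjusted, rho 0.8, c = 0.5 |
|---|---|---|---|---|---|---|
| 0.5 | 25% (18.7) | 30.8% (20.2) | 36.1% (21.9) | 12.5% (16.0) | 15.1% (16.5) | 17.6% (17.0) |
| 0.7 | 15% (16.5) | 22.0% (17.9) | 29.9% (20.0) | 7.5% (15.1) | 10.8% (15.7) | 14.6% (16.4) |
| 0.9 | 5% (14.7) | 9.2% (15.4) | 16.0% (16.7) | 2.5% (14.4) | 4.6% (14.7) | 8.0% (15.2) |
| 0.95 | 2.5% (14.4) | 4.9% (14.7) | 9.4% (15.5) | 1.25% (14.2) | 2.5% (14.4) | 4.7% (14.7) |

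**Scale of the gain.** For a two-sample t-test with 7 per arm, the difference detectable with 80% power is 1.63 single-read SDs. In the unadjusted, independent-error case this becomes 1.63 x sqrt(0.75) = 1.41 at R = 0.5 and 1.63 x sqrt(0.95) = 1.59 at R = 0.9. The sample size stays the main limit.

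**Precision of the reliability figure.** Take the 14 subjects at one visit, two reads each, and an observed ICC of 0.7. Then F = 1.7/0.3 = 5.67 on 13 and 14 degrees of freedom. Dividing F by 3.01 and multiplying it by 3.08 (the 97.5% F points), then converting by (F - 1)/(F + 1), gives a 95% interval of about 0.31 to 0.89. Using all 56 pairs of reads gives about 55 degrees of freedom for the within-reader error SD, or roughly -16% to +23%. That assumes independent normal errors, and the four images per subject are clustered.

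**Timing of scoring.** Section 9 places scoring after all subjects finish. Section 7 lists both evaluations at every visit, and section 12 reviews scale scores after each visit. Scores made only at the end cannot be reviewed after each visit. Either an on-site score also exists, or one of these statements needs changing.

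**The case against.** The strongest case against is that a single read is not an error in a pilot, and that the benefit is uncertain. Section 9 calls both scales validated. If this reader is highly repeatable, little is gained: at R = 0.95 the cut is 2.5% unadjusted and 4.9 to 9.4% adjusted, even with independent errors. Section 11 names no baseline-adjusted model, only an appropriate test against baseline, so the larger figures rest on an analysis that the plan does not specify. The images are faces of 14 people, four sets each. A reader can recognise them and recall scores, which shrinks the gain and makes the ICC look better than it is. All of this stands, and it is why the size is given as a range and not as one figure. The validated label, however, does not say how repeatable this reader is on these images.

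A reader might infer three stronger claims that the documents do not support:

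- **That the protocol fixes one read per photograph.** It fixes the number of evaluators and is silent on the number of reads. The text in sections 7 and 12 also leaves open whether a separate on-site score exists.
- **That a second read would certainly make a marked difference.** No reliability is given, so it may or may not.
- **That re-reading would remove bias.** It reduces only random within-reader error. Reader-specific bias, photograph-to-photograph variation and any effect of knowing the arm all remain.

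**Conclusion.** The point holds as an optional, low-cost improvement, with low confidence about its size. The plan specifies no repeat read and no intra-rater reliability check for a subjective primary score, in a pilot whose purpose is to inform a later study.

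For assumed single-read reliability of 0.5 to 0.9 and independent errors, a second averaged read cuts MoPASI variance by about 5 to 25% unadjusted, or 9 to 36% baseline-adjusted at true correlation 0.6 to 0.8. With errors correlated at 0.5 it gains about half as much. The reliability, the correlations and the baseline-adjusted model are assumptions; no dropout is assumed either.

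The firmer benefit is a reliability figure where the plan provides none, though 14 subjects will estimate it imprecisely. The conflict over when scores are made, and so which scores are analysed, is a matter of the text alone and needs no assumption.

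**What to change.** In section 9, add that the same evaluator scores every photo set a second time, at least two weeks after the first read, in fresh random order and without access to the first scores. Arm and visit labels should be removed for MoPASI. The subject cannot reliably be hidden on a facial photograph, so the text should not promise that. In section 11, state that the mean of the two MoPASI reads is analysed and that the intra-rater ICC is reported with its confidence interval. Report the single-read SD as well, so that a later study can plan for either number of reads.

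GAIS needs the baseline photograph for comparison. It can be re-read in the same session with arm hidden, once that session's MoPASI scores are recorded.

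Reconcile sections 7, 9 and 12 so that it is clear whether scores are also made at visits and which scores enter the primary analyses.

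The cost is evaluator time for about 56 more readings (14 x 4), taking the total from 56 to 112, with no extra reader, visit or procedure. Section 7 allows four months after the subjects finish, so a two-week gap fits.
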